9.2 Reporting to the IRB

In addition to the continuing review reports to the IRB, the Principal Investigator is responsible for reporting all serious **and** unexpected adverse events that impact the safety of risk to study research participants. Unexpected death will be reported to the IRB office immediately at SJCRH. Serious unexpected events will be reported within 48 hours, and all others within 10 working days.

9.3 Emergency Unblinding

In the case of a medical emergency or in the event of a serious medical condition, when knowledge of the investigational product is essential for the clinical management or welfare of the subject, an investigator or other physician managing the subject may decide to unblind that subject's treatment code.

The physician managing the medical emergency or serious condition should attempt to contact the principal investigator to discuss options prior to unblinding, and the principal investigator should approve the unblinding, when applicable. However, ensuring patient safety is the primary objective when the decision to unblind the treatment assignment is made.

The principal investigator or designated study personnel will complete an off therapy request with the rationale to unblind study drug listed. The principal investigator or designated study personnel will contact pharmacy to determine the unblinding information.

Any patient whose treatment assignment is unblinded will be removed from study treatment and followed off-therapy. The study team will continue to follow the patient status regarding the serious adverse event(s) for which the patient's treatment was unblinded until resolved or improved to baseline. The patient can receive off-study treatment as necessary.

All occurrences of emergency unblinding will be reported to the IRB according to the criteria established in protocol section 9.0, and the FDA, when applicable.

9.4 Criteria for Unblinding

The occurrence of a serious adverse event that is both unexpected and considered by the reporting investigator to be associated with the use of study drug, and the knowledge of the treatment assignment is deemed essential for the patient's care in treatment of the event. This criteria includes known overdose of study drug.

10.0 DATA COLLECTION, STUDY MONITORING, AND CONFIDENTIALITY

10.1 Data Collection

A member of the TINALL study team will complete documentation in MILLI for each study encounter (“anesthesia research note”). Data will then be entered into a secure database, which serves as the electronic case report forms (eCRFs). Records from the study which identify the study participant will be kept confidential in a secured area.

10.2 Study Monitoring

Source document verification of eligibility for all SJCRH cases will be performed within two weeks of completion of enrollment. This will include verification of appropriate documentation of consent. Monitoring of timeliness of adverse and serious adverse event reporting will be done as events are reported. Monitoring of protocol compliance, adverse event reporting, and data completeness will be conducted according to recommended schedule for this study.

10.3 Confidentiality

Study numbers will be used in place of an identifier such as a medical record number. No research participant names will be recorded on the data collection forms. The list containing the study number and the medical record number will be maintained in a locked file and/or in a password protected database and will be destroyed after all data have been analyzed.

The medical records of study participants may be reviewed by the St. Jude IRB, FDA, clinical research monitors, etc.

11.0 STATISTICAL CONSIDERATIONS

11.1 Primary Objective

This study has the following single primary objective:

To assess the analgesic efficacy of gabapentin in controlling VCR-related NP/PN in participants with ALL, as reflected by the morphine daily dose (mg/kg/day) used to control NP/PN as a primary or a rescue regimen, and by daily pain scores in the gabapentin vs. placebo groups.

Accrual: The eligibility criteria requires that a patient can be enrolled in this study only if a VCR-induced NP not previously treated by gabapentin occurred after vincristine doses administered at the following time points: Induction Week 1 ± 3 days, Induction week 2 ± 3 days, Continuation Week 7 (Re-induction I) ± 3 days or Week 17 (Re-induction II) ± 3 days of Continuation. A review of Total XVI or “as per TOTXVI” patients up to the date of this protocol development showed that respectively 33, 29, 5, and 1 patient satisfied the condition at the time points. A review of Total XV showed a similar pattern. Thus we expect to enroll for this study at least 60 patients in the remainder of Total XVI or “as per TOTXVI. We will enroll and randomize all eligible and consented patients in the remainder of Total XVI or “as per TOTXVI”. To achieve a total of 60 evaluable patients, up to 80 participants may be enrolled.

Study Design: Placebo-controlled, randomized Phase-II trial. Sixty (60) participants will be randomized into the treatment (gabapentin) and the placebo group, with 30 patients per group.

Analysis: For each subject a pre-treatment (baseline) pain score will be obtained from the leukemia clinic. This score serves as the baseline level of pain and is used in stratified randomization (see below); and if necessary, as a covariate in modeling the daily morphine dosage used for pain control. The daily morphine dosage will be modeled as longitudinal observations with treatment (gabapentin vs. placebo) group, and if necessary, other clinical factors such as age category for pain assessment (0-3yr, 4-7yr, >7yr), baseline pain score, and ALL risk classification, as explanatory factors, using repeated measure linear models.

Multiple test adjustment will not be made. Participants **whose doses of vincristine are delayed or those who are taken off study drug** will be included in the analysis according to “intent to treat”.

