Patients with ALL on Total XVI or "as per TOTXVI" who experience NP/PN after specific doses of vincristine are eligible to enroll in the study as soon as the diagnosis of NP/PN related to VCR is established. The qualifying doses of vincristine have been selected because they fall in the schedule of weekly vincristine doses as per Total XVI, and 2 additional weekly vincristine doses are anticipated according to the protocol. Participants will be randomized to receive gabapentin or placebo upon enrollment. Morphine will be available to both groups as needed for pain at any time on the study. At the time of enrollment, and daily thereafter until completion of the study drug, data will be collected for pain assessment, and the daily dose of oral morphine used will be collected. Data regarding the pain type, quality, and location, as well as treatments used to manage pain will be assessed on a daily basis for the diagnostic event and for the period following the next two administrations of VCR treated with the study drug.

Objectives:

Primary Objective:

To assess the analgesic efficacy of gabapentin in controlling VCR-related NP/PN in participants with ALL, by comparing the morphine daily dose (mg/kg/day) used to control NP/PN as a primary or a rescue regimen in the gabapentin vs. placebo groups.

Secondary Objective:

To compare the pain scores in the gabapentin and placebo groups as recorded by pain score right now and pain score average for previous 24 hours.

Responsible Investigator: [name]

Statistician: [name].

Estimated date for completion of data collection: December 2015

TINALL - Therapeutic Interventions for Peripheral Neuropathy/Neuropathic Pain Induced by Vincristine Treatment for Childhood ALL on Total XVI Protocol

Hypotheses/Estimates: The hypothesis is that treatment with gabapentin has better analgesic efficacy than placebo in the treatment of VCR-related NP/PN. Based on the current enrollment on the Total XVI protocol, the projected enrollment, the incidence of NP/PN of 34.9% as determined in our previous study of NP/PN associated with the Total XV protocol, we estimate that 60 study participants will be eligible to enroll in this study during the duration of the Total XVI study. To achieve a total of 60 evaluable patients, up to 80 participants may be enrolled.

Criteria for Evaluation:

Safety: Any adverse events will be recorded and reported.

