Appendix I: Example of a schedule of evaluations

Appendix II: Research Activities

Appendix III: Pain Scales

1.0 **OBJECTIVES**

The investigators propose to study the analgesic efficacy of gabapentin for the treatment of neuropathic pain/peripheral neuropathy (NP/PN) associated with vincristine therapy in the context of treatment of childhood ALL on Total XVI protocol.

1.1 **Primary Objective**

To assess the analgesic efficacy of gabapentin in controlling VCR-related NP/PN in participants with ALL, by comparing the morphine daily dose (mg/kg/day) used to control NP/PN as a primary or a rescue regimen in the gabapentin vs. placebo groups.

1.2 **Secondary Objective**

To compare the pain scores in the gabapentin and placebo groups as recorded by pain score right now and pain score average for previous 24 hours.

2.0 **BACKGROUND AND RATIONALE**

2.1 **Background**

Children with cancer experience a significant symptom burden during the course of treatment^{1,2}, and pain is the most frequent, most severe and most distressful of symptoms. The impact of pain experienced during treatment for cancer has long term implications after completion of therapy^{3,4}.

Neuropathic pain and related neuropathy symptoms have been directly correlated with chemotherapeutic agents⁵, vincristine in particular⁶ and have been reported during therapy for childhood cancers^{7,8}.

Neurotoxicity, the dose-limiting side effect of vincristine, most often causes mixed sensorimotor neuropathy (loss of deep tendon reflexes, paresthesias, neuritic pain, and wrist or foot drop) or autonomic neuropathy (constipation, abdominal pain, paralytic ileus, bladder atony with retention of urine, and orthostatic hypotension). On the rare occasions in which vincristine-associated neurotoxicity involves the cranial nerves, it produces transient cortical blindness, oculomotor nerve dysfunction with ptosis and diplopia, jaw pain, facial palsy, hearing loss, and vocal cord paresis or paralysis⁵.

The incidence of peripheral neuropathy related to vincristine during treatment of childhood ALL per protocol Total XIIIB in our institutional experience has been 17.5% (42 of 240)⁹ and peripheral neuropathy/neuropathic pain were identified as adverse events in 34.9% of

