multilevel orthopedic surgery¹⁴, and 10-30 mg/kg/day in 5 children with cancer-related pain (n=4) or neuropathic neck pain (n=1)¹².

Dosing and safety information for the pediatric use of gabapentin has been defined only for anti-seizure therapy²⁰. Most pediatric pain specialists recommend the anti-seizure dose regimen for children with NP, starting at 10 mg/kg/day and titrating upward to 50 to 70 mg/kg/day. Gabapentin is currently the first-line therapy for NP at our institution. In our retrospective review of neuropathic pain during Total XV protocol for ALL at St. Jude, we found treatment data for 180 of 207 episodes of NP in 153 of 174 patients; the missing data reflect treatment at a site other than St. Jude. Gabapentin was used to treat 62.2% of episodes (112 of 180) in 65.4% of patients (100 of 153); the remaining 37.8% of episodes (68 of 180) in 34.6% of patients (53 of 153) were treated with opioids. The selection of gabapentin or opioids did not appear to be influenced by the pain intensity score at the time of diagnosis of NP (p=0.91). The mean starting dose used for the 112 episodes was 15.5 mg/kg/day (SD 7.9)¹⁰. In this study we found the median starting dose to be 14.2 mg/kg/day. In the absence of a uniform approach to the use of gabapentin, prospective studies are needed to determine the optimal regimen. There is some evidence that concurrent use of gabapentin and morphine provide better analgesia at doses lower than those used for single-agent therapy¹¹.

The duration of gabapentin therapy of up to 21 days is based on the pattern of administration of the trigger agent for neuropathic pain in ALL. We have selected the phases of the Total XVI or “as per TOTXVI” protocol during which VCR is administered most intensely, in weekly doses. Indeed, data from Total XV and preliminary data from Total XVI or “as per TOTXVI support the highest cumulative incidence of neuropathic pain at the time of induction, reinduction I and II. The duration of gabapentin therapy reflects the duration of vincristine administration.

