11.2 Randomization

Randomization will be performed in SJCRH pharmacy by a research pharmacist, using the randomization program developed by the Department of Biostatistics. The randomization will be stratified by the three age categories for which distinct pain assessment tools are applied, and by two categories of the baseline pain score (<5, ≥5). The joint distribution of the age and baseline pain score categories in the enrolled

patients may be skewed with either null or small odd-numbered (1, 3, 5) cell sizes, and consequently stratification may still not able to guarantee balance. If it so happens, the age categories and baseline pain score will be included in the longitudinal model as covariates (see above).

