APPENDIX II
RESEARCH ACTIVITIES

Study day	Confirm enrollment criteria	Informed consent	Randomization	VCR dose (expected or actual)	Pain score right now	Average Pain for 24h	Pain location	Pain descriptor	Order Morphine PRN	Study drug TID	Assess opioid use	Assess study drug use	Assess AE	Off Study
pre-enrollment				actual										
Diagnosis of NP (any day between 1 and 7)	x	x	x		x	x	x	x	x	x	x	x	x	
					x	x	x	x	x	x	x	x	x	
					x	x	x	x	x	x	x	x	x	
					x	x	x	x	x	x	x	x	x	
					x	x	x	x	x	x	x	x	x	
7				expected	x	x	x	x	x	x	x	x	x	x
8					x	x	x	x	x	x	x	x	x	x
9					x	x	x	x	x	x	x	x	x	x
10					x	x	x	x	x	x	x	x	x	x
11					x	x	x	x	x	x	x	x	x	x
12					x	x	x	x	x	x	x	x	x	x
13					x	x	x	x	x	x	x	x	x	x
14				expected	x	x	x	x	x	x	x	x	x	x
15					x	x	x	x	x	x	x	x	x	x
16					x	x	x	x	x	x	x	x	x	x
17					x	x	x	x	x	x	x	x	x	x
18					x	x	x	x	x	x	x	x	x	x
19					x	x	x	x	x	x	x	x	x	x
20					x	x	x	x	x	x	x	x	x	x
21					x	x	x	x	x	x	x	x	x	x

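### Pre-treatment opioid use is not a prespecified covariate for the morphine endpoint, and the enrollment day is not assigned to baseline or outcome

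*Combined protocol and SAP*

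**What the plan says.** The primary objective (section 1.1) is to assess efficacy "by comparing the morphine daily dose (mg/kg/day) used to control NP/PN as a primary or a rescue regimen in the gabapentin vs. placebo groups". Section 11.1 fits a repeated-measures linear model to the daily dose, with treatment group as its one definite term. The possible further terms, to be added only where needed, are "other clinical factors such as age category for pain assessment (0-3yr, 4-7yr, >7yr), baseline pain score, and ALL risk classification, as explanatory factors". Baseline pain is likewise to be used "if necessary, as a covariate in modeling the daily morphine dosage used for pain control". Section 11.2 supplies the only trigger. It warns that stratification by age and baseline pain may not achieve balance, and continues: "If it so happens, the age categories and baseline pain score will be included in the longitudinal model as covariates". Nowhere does section 11 mention opioid use before treatment.

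On data collection, the Brief Outline of Treatment Plan says that data are gathered from enrollment onward, "and the daily dose of oral morphine used will be collected". Appendix II has a column headed "Assess opioid use", first marked on the row for the day of NP diagnosis. Randomization and study drug are marked on that same row, while the pre-enrollment row shows only the vincristine dose. Appendix I puts the morphine prescription and the start of study drug at the same step. It lists a baseline pain assessment but no baseline opioid assessment.

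**The concern.** When the outcome is a quantity that can be measured before treatment, its baseline value is the natural first candidate for adjustment. Here the plan names three other covariates, makes all of them conditional, and does not mention this one. Participants can plausibly differ at entry: earlier gabapentin is an exclusion (section 3.2) but earlier opioid use is not, and enrollment may fall on any of days 1 to 7 after the qualifying vincristine dose (Appendix I). Randomization is stratified by age and pain only, so opioid use at entry is left to chance.

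Two things are at stake. The first is precision: the target of 60 comes from projected accrual rather than a power calculation, so there is no stated margin to absorb avoidable variance. The second is definition: the synopsis analyzes average daily morphine over a treatment period of at most 21 days without saying whether the enrollment day counts. A conditional, open covariate list also leaves the form of the primary model to be settled after data have been seen.

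**Working it through.** **Plan's own figure.** There is none to reproduce. The documents give no alpha level, power, effect size or standard deviation (SD) for morphine dose.

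**Inputs from the documents.** 30 per arm, N = 60 (section 11.1); one-sided test (synopsis, Data Analyses); treatment to day 21 with entry on any of days 1 to 7 (Appendices I and II).

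**Inputs assumed.** One-sided alpha 0.05; correlation r between pre-treatment opioid use and mean on-study morphine, over the range 0 to 0.7.

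**Step 1: reference effect.** The difference detectable with 80% power and no adjustment is (1.645 + 0.842) × √(2/30) = 0.64 SD.

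**Step 2: effect of adjustment.** Relative variance of the treatment effect = (1 - r²) × (1 + 1/(N - 4)). The second term is the approximate cost of estimating the covariate: 1 + 1/56 = 1.018. Equivalent patients per arm = 30 divided by the relative variance. Power is taken at 0.64 SD.

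| r | 1 - r² | Relative variance | Change | Equivalent per arm | Power |
|---|---|---|---|---|---|
| 0 | 1.00 | 1.018 | +2% | 29.5 | 79.4% |
| 0.3 | 0.91 | 0.926 | -7% | 32.4 | 82.6% |
| 0.5 | 0.75 | 0.763 | -24% | 39.3 | 88.5% |
| 0.7 | 0.51 | 0.519 | -48% | 57.8 | 96.5% |

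At one-sided 0.025 (reference effect 0.72 SD) the powers are close: 79.3%, 82.9%, 89.4% and 97.3%.

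**Step 3: baseline pain already in the model.** Let p be the correlation of pain with the outcome, m that of baseline opioid use with the outcome, and c that between the two covariates. Then R² = (p² + m² - 2pmc)/(1 - c²), and the further cut is 1 - (1 - R²)/(1 - p²). These figures omit the covariate cost.

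- p = 0.3, m = 0.3, c = 0.5: R² = (0.09 + 0.09 - 0.09)/0.75 = 0.12; further cut 1 - 0.88/0.91 = 3%.
- p = 0.4, m = 0.6, c = 0.5: R² = (0.16 + 0.36 - 0.24)/0.75 = 0.373; further cut 1 - 0.627/0.84 = 25%.

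The other sets tried lay between these two.

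**Step 4: many participants at zero.** Baseline use was simulated as a normal variable cut off at zero, with underlying correlation 0.5 and no covariate cost. The variance cut falls from 25% with none at zero to 18% with half, 14% with 70% and 7% with 90% at zero.

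**Step 5: the enrollment day.** Entry on day 1 gives 21 treatment days and entry on day 7 gives 15 (days 7 to 21). One undefined day is therefore 1/21 = 5% to 1/15 = 7% of the averaging period.

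**The case against.** The strongest reply is that nothing here is an error. An unadjusted randomized comparison is valid, and its error rate already allows for chance imbalance. Baseline pain is a stratification factor, and as-needed morphine is taken for pain, so part of the variation is already handled. Participants enroll as soon as NP/PN is diagnosed and the study's morphine is ordered at that point, so many may enter on no opioid and the covariate would then carry little. Use before entry may also be of another opioid, or at another site. All of this stands, and it limits the gain, as steps 3 and 4 show. It does not remove the case for a term that costs about 2% in variance if it proves useless.

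A reader might go further in several ways that the documents do not support:

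- **That baseline morphine is already collected and has been excluded.** The list is open, so the variable is unnamed rather than ruled out. The enrollment record is not shown to precede study drug, and a dose total that includes time after the first dose is not a proper baseline.
- **That past practice shows wide opioid use at entry.** Section 2.2 reports that "the remaining 37.8% of episodes (68 of 180) in 34.6% of patients (53 of 153) were treated with opioids", but this describes how Total XV episodes were treated, not what patients had taken before enrolling in a trial.
- **That the trial forgoes the equivalent of nearly doubling its size.** That follows only at r = 0.7, against a model with no adjustment.
- **That imbalance at entry biases the result.** It adds variance, not systematic error.

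**Conclusion.** The point holds as a low-cost improvement to the primary analysis. Section 11.1 does not prespecify pre-treatment opioid use, makes the covariates it does name conditional, and leaves the enrollment day undefined. These three observations rest on the text alone.

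The size of the gain does not. It rests on a correlation that the documents do not give. Power moves from 80% by -0.6 points at r = 0 and by +2.6, +8.5 and +16.5 points at 0.3, 0.5 and 0.7. If r is about 0.3 or more, the gain is worth having at 30 per arm; if nearly everyone enters on no opioid, it will be small. The enrollment-day ambiguity is modest in size, but it is an open rule for the primary endpoint and should be closed whatever the correlation.

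**What to change.** 1. Add one field to the enrollment note: opioid use in the 24 hours before the first study-drug dose, in mg/kg of oral morphine, with other opioids converted to morphine equivalents by a stated table. Because the study drug is blinded and not yet taken, this value cannot depend on assignment. Say how a missing value will be handled, since some earlier care may have been given elsewhere.
2. In section 11.1, replace the conditional wording for the primary model with a fixed list: treatment, pre-treatment opioid use, and the two stratification factors (age category and baseline pain). Any further factor belongs in a sensitivity analysis.
3. State that outcome days begin after the first study-drug dose, so that no record serves as both baseline and outcome. Align Appendices I and II with this.

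The cost is one data field, some opioid conversion, a few sentences and one degree of freedom for the added covariate. No extra visits or participants are needed.

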11.2 Randomization

Randomization will be performed in SJCRH pharmacy by a research pharmacist, using the randomization program developed by the Department of Biostatistics. The randomization will be stratified by the three age categories for which distinct pain assessment tools are applied, and by two categories of the baseline pain score (<5, ≥5). The joint distribution of the age and baseline pain score categories in the enrolled

patients may be skewed with either null or small odd-numbered (1, 3, 5) cell sizes, and consequently stratification may still not able to guarantee balance. If it so happens, the age categories and baseline pain score will be included in the longitudinal model as covariates (see above).

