11.3 Secondary Objective

Daily “pain score right now” and “pain score average last 24 hours” will be compared between the gabapentin and place groups using longitudinal models, with pain treatment group and if necessary, other clinical factors as explanatory variables. For “pain score right now”, time since last morphine use will be used as an explanatory variable as well. The pain scores are discrete, thus a proper link function (such as Poisson) will be applied.

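### Age category and baseline pain stratify the randomisation but enter the models only conditionally; leaving them out when stratification has worked makes the test conservative if they are prognostic

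*Combined protocol and SAP*

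**What the plan says.** Section 11.2 states: "The randomization will be stratified by the three age categories for which distinct pain assessment tools are applied", and adds two categories of baseline pain cut at 5. That makes 3 × 2 = 6 strata for 60 patients.

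The analysis text does not carry these factors through.

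- **Section 11.1, morphine model.** Treatment is the only group-comparison term that always enters. Baseline pain is used for stratification, "and if necessary, as a covariate in modeling the daily morphine dosage used for pain control". Age comes in on the same footing: "and if necessary, other clinical factors such as age category for pain assessment". Section 11.1 gives no criterion for either.
- **Section 11.2.** This holds the one stated trigger. The cross-classification of age and baseline pain "may be skewed with either null or small odd-numbered (1, 3, 5) cell sizes", so stratification might fail to balance the arms. Then: "If it so happens, the age categories and baseline pain score will be included in the longitudinal model as covariates".
- **Section 11.3, pain-score models.** These are fitted "with pain treatment group and if necessary, other clinical factors as explanatory variables". Neither stratification factor is named.

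**The concern.** Stratified randomisation removes between-stratum differences from the treatment comparison. A model without the stratification factors leaves those differences in its residual variance. The reported standard error then describes a noisier experiment than the one that was run, and the test rejects too rarely. The remedy is to keep the factors in the model when stratification has succeeded. The plan ties inclusion to the opposite case, when stratification may not have balanced the arms.

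The trigger is also open to two readings. Adjustment may follow from the mere presence of a cell of a listed size, or it may need an actual imbalance, for which no limit is set.

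At stake is power in a trial with about 30 patients per arm, whose size rests on expected incidence and not on a power calculation (Protocol Summary, Sample Size). The model also remains partly open until the data are in hand.

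**Working it through.** **Inputs from the documents.** 60 evaluable patients, 30 per arm (11.1); six strata (11.2); a one-sided alternative (Protocol Summary, Data Analyses); a repeated-measures linear model for morphine (11.1). The plan states no standard error, alpha, effect size or power, so there is no figure of its own to reproduce.

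**Assumptions.** One-sided alpha 0.05; permuted blocks of 4; patient-level mean outcome with total SD 1. R² is the share of between-patient variance explained by the factors, varied from 0 to 0.5. The effect is the one detectable with 80% power by an unadjusted normal approximation: (1.645 + 0.842) × √(2/30) = 0.64 SD.

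**Step 1: formula, perfectly balanced strata.** The true variance of the unadjusted difference falls by the factor (1 − R²), but its reported SE stays at √(2/30) = 0.258. Hence reported SE / true SE = 1/√(1 − R²), and one-sided size = 1 − Φ(1.645/√(1 − R²)).

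| R² | SE ratio | Size at nominal 0.05 |
|---|---|---|
| 0 | 1.00 | 0.050 |
| 0.1 | 1.05 | 0.042 |
| 0.2 | 1.12 | 0.033 |
| 0.3 | 1.20 | 0.025 |
| 0.5 | 1.41 | 0.010 |

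Simulation with blocks of 2 or 4 and even or skewed strata (4,000 trials per scenario) gives unadjusted size 0.039–0.049, 0.026–0.028 and 0.012–0.015 at R² 0.1, 0.3 and 0.5. The stratum-adjusted model gives 0.044–0.057 throughout. Without stratified randomisation the unadjusted test stays at 0.044–0.049, so the conservatism comes from stratifying and then not adjusting.

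**Step 2: the rule as written.** I coded one reading of 11.2: adjust if any of the six cells holds 0, 1, 3 or 5 patients. The adjusted model has treatment, age (three levels) and continuous baseline pain; 20,000 trials per scenario. With stratum shares 10/10/15/15/25/25% the trigger is met in 54% of trials.

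| R² | Power: never | As written | Always |
|---|---|---|---|
| 0 | 79.2% | 79.0% | 78.8% |
| 0.05 | 79.3% | 79.8% | 80.3% |
| 0.15 | 80.1% | 82.2% | 84.1% |
| 0.30 | 82.1% | 86.4% | 89.7% |
| 0.45 | 84.2% | 89.8% | 95.0% |

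At R² 0.30 the true SD of the estimate is 0.228 unadjusted and 0.219 adjusted (0.228/0.219 = 1.04), while the mean reported SE is 0.258 against 0.216 (0.258/0.216 = 1.19). The loss is thus mainly in the reported SE; the estimate itself is barely less precise. Type I error is 3.0% never, 4.0% as written, 4.9% always.

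**Step 3: sensitivity to stratum shares, R² 0.30.**

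| Shares | Trigger met | As written | Always | Loss (points) |
|---|---|---|---|---|
| Equal | 21% | 83.6% | 89.8% | 6.2 |
| 10/10/15/15/25/25% | 54% | 86.4% | 89.7% | 3.3 |
| 5/5/15/15/30/30% | 80% | 88.1% | 89.6% | 1.5 |

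The loss is largest where the strata are well filled, because the trigger is then met least often.

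**Step 4: pain scores.** A quasi-Poisson log-link model on patient totals (assumed: 18 days, mean score 3, between-patient log SD 0.6; 8,000 trials; shares 10/10/15/15/25/25%) gives power of 73.0/72.8/72.6% at R² 0 and 76.2/81.0/84.6% at R² 0.30, for never / as written / always. Type I error at R² 0.30 is 2.9/3.7/4.8%.

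**The case against.** Several points can be made for the plan.

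- **A trigger exists.** Section 11.2 lists cell sizes and cross-refers to 11.1, so for these two factors the condition in 11.1 is partly defined. This stands: the defect is an ambiguous trigger with no limit for imbalance, not the absence of any rule. It does not help where the strata fill well, since adjustment is then not required.
- **11.2 may extend to 11.3.** It speaks of the longitudinal model, and 11.3 also uses longitudinal models. The text does not settle this.
- **The effect needs prognostic factors.** This stands. Nothing in the documents shows how well age or baseline pain predicts morphine per kilogram. At R² 0.05 the written rule loses about half a point, and at 0.15 about two with the intermediate shares.
- **The baseline is assumed.** Alpha, block size, effect and stratum shares are not in the plan, and a patient-mean model stands in for the repeated-measures one. The direction is secure; the magnitudes are illustrative.
- **The error is on the safe side.** This is true of omission under a fixed rule. If the analyst could choose between the adjusted and unadjusted result after seeing both, size at nominal 5% would rise to about 5.3–5.4% (R² 0 to 0.10). That is small, but it is a further reason to settle the choice in advance.

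**Conclusion.** The concern holds. The plan stratifies on two factors, permits adjustment for them, and does not commit to it; read literally, adjustment can lapse when stratification has succeeded. If the factors are prognostic, the unadjusted test is then conservative.

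Under the assumptions above, the written trigger gives up about 1.5 to 6 power points against always adjusting at R² 0.30. Never adjusting gives up about 8 points at that R², and about 11 at R² 0.45 (95.0 − 84.2). With no prognostic value there is no loss. Confidence is high in the reading of the text and in the direction, and lower in any single magnitude. This is a change that should be made; it does not threaten the validity of a positive result.

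**What to change.** In 11.1, 11.2 and 11.3, replace the conditional wording for these two factors with:

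> Age category (three levels) and baseline pain score (continuous, 0–10, the same score used for stratification) are always included as covariates in the primary morphine model and in both secondary pain-score models, whatever the observed balance.

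Naming the stratification score also settles which baseline is meant: 11.1 takes it from the leukemia clinic, whereas Appendix I lists a baseline assessment by the study team.

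The cost is three covariate degrees of freedom (two for age, one for pain) on data already collected. At R² 0 that is 79.2 − 78.8 = 0.4 points of power. The wording does not cover ALL risk classification or the unnamed clinical factors, which stay conditional unless they too are fixed in advance or confined to sensitivity analyses. It also assumes one slope for baseline pain across the three pain instruments, which a sensitivity analysis could check.
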